**Secondary objectives:**

- Comparison of the quantitative amount of hemo/myoglobin and collagen signal determined by MSOT in muscle tissue of healthy volunteers at timepoint 1 and timepoint 2 after two weeks
- Comparison of the quantitative proportion of oxygenated/deoxygenated hemo/myoglobin signal in muscle tissue of healthy volunteers at timepoint 1 and timepoint 2 after two weeks
- Comparison of the MSOT-determined quantitative amount of hemo/myoglobin and collagen signal at three muscle positions of two muscles (quadriceps femoris and gastrocnemius)
- Comparison of the quantitative proportion of oxygenated/deoxygenated hemo/myoglobin signal determined by MSOT in three muscle positions of two muscles (quadriceps femoris and gastrocnemius)
- Comparison of the quantitative proportion of hemo/myoglobin and collagen signal determined by MSOT in muscle tissue of healthy female and male volunteers
- Comparison of the quantitative proportion of oxygenated and deoxygenated hemo/myoglobin signals determined by MSOT in muscle tissue of healthy female and male volunteers
- Correlation of the hemo/myoglobin and collagen signal determined with MSOT with the 6-MWT
- Correlation of the oxygenated/deoxygenated hemo/myoglobin signal determined by MSOT with the 6-MWT
- Comparison of the quantitative amount of hemo/myoglobin and collagen signal determined by MSOT between two independent examiners

- Comparison of the quantitative amount of hemo/myoglobin and collagen signal determined by MSOT between two images of one examiner

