## 7. Target parameters

All measurements with MSOT are performed at three muscle positions of the proximal and distal lower extremity muscles in lateral comparison (right - left, leg proximal: Musculus quadriceps, distal: Musculus gastrocnemius) by two different examiners, in healthy subjects, at two different timepoints.

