### **Participant number**

As this is a pilot study, it is not possible to calculate the exact number of cases. It is planned to examine a total of 10 healthy volunteers.

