### Measurements

[figure not shown]
After informing of the subjects, all study participants are imaged by MSOT at 3 positions of 2 anatomical muscle regions on both sides (right and left): upper/lower leg, on predefined muscle groups (leg proximal: Musculus quadriceps, distal: Musculus gastrocnemius). The examination is performed by two independent examiners directly one after the other. The examination is performed analogous to sonography over the corresponding skin layers without further invasive procedures. The anatomical region can be localized by means of built-in B-scan sonography; the corresponding optoacoustic signals can be recorded in parallel. Each examiner performs two repetitive scans per muscle position. The duration per anatomical region is limited to 5 minutes; this corresponds to a maximum of 20 minutes for both lower extremities. The subjects can remain in a relaxed body position during the examination; assistance in the form of breathing manoeuvres or similar is not necessary. Subsequently, a 6-minute walk test is performed to test muscle activation. Afterwards another examination with MSOT is carried out analogous to the above mentioned procedure. The same procedure is repeated after 14 days.

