Non-invasive molecular imaging to determine the hemoglobin and collagen content in muscles before and after physical exercise and over time (MSOT_muscles)

Unique Protocol ID: 169_19B

ClinicalTrials.gov Identifier: NCT03979157

Version date: 23.04.2019

Sponsor:

Department of Pediatrics and Adolescent Medicine
University Hospital Erlangen
Friedrich-Alexander-University (FAU) Erlangen-Nürnberg
Pediatric Experimental and Translational Imaging Laboratory (PETI-Lab)
[name]
[name]
[contact]

Statistical Analysis Plan

The present study is a pilot proof-of-concept study. Due to lack of clinical trials in this area, the comparative changes of MSOT spectra and signals within and between examiners, before and after exercise, over time and between different muscles and muscle positions are unknown. Therefore, no sample size calculation was performed.

The primary outcome measure is to assess the reproducibility of the muscular optoacoustic spectra of healthy volunteers facing different variables (examiner, time, exercise, muscle position).

MSOT signals are derived from averaged video captures (seven frames) obtained in anatomical independent muscle regions in patients. All anatomical locations are considered independent. In cases of multiple scans/recordings, a mean of all analyzed scans is calculated.

Continuous variables are given as means and standard deviations; categorical variables are provided as numbers and percentages. Data are tested for normal distribution using Shapiro-Wilk test prior to inferential analysis. MSOT signals are compared matched manner using a paired t-test when parametric and a Wilcoxon matched-pair signed rank test when non-parametric. For the comparison of three or more groups analysis of variance (ANOVA) and for nonparametric distribution Friedman Test is used. Correlations are specified with the parametric Pearson correlation coefficient (r) and the nonparametric Spearman correlation (r_s), using a 95% confidence interval. Additionally, the intraclass correlation coefficient (ICC) will be used with the grading proposed by Landis and Koch. For all analysis an error level of $p < 0.05$ is considered as statistically significant. All analyses are performed using GraphPad Prism (Version 8, GraphPad Software, La Jolla, CA, USA) and/or IBM SPSS Statistics (Version 24, IBM Corp., N.Y., USA).

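### The SAP treats all anatomical locations as independent, although each volunteer contributes 12, and states no unit of analysis or n; if locations are pooled, the error rates of the 6-MWT correlation and the female-male comparison are not controlled

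*SAP*

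**What the plan says.** The SAP's rule is "All anatomical locations are considered independent". The only averaging it describes concerns repeat recordings: "In cases of multiple scans/recordings, a mean of all analyzed scans is calculated". It then names paired t-tests and Wilcoxon tests, followed by "For the comparison of three or more groups analysis of variance (ANOVA) and for nonparametric distribution Friedman Test is used" and "Correlations are specified with the parametric Pearson correlation coefficient (r) and the nonparametric Spearman correlation (r_s), using a 95% confidence interval", and an intraclass correlation coefficient (ICC). No n, no unit of analysis and no clustered or mixed model appears. Protocol section 12 does not supply them either.

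On the layout, Protocol section 7 states: "All measurements with MSOT are performed at three muscle positions of the proximal and distal lower extremity muscles in lateral comparison". Section 10 (Measurements) gives the same scheme. Section 9 (Participant number) says "It is planned to examine a total of 10 healthy volunteers". The secondary objectives in section 6 include "Correlation of the hemo/myoglobin and collagen signal determined with MSOT with the 6-MWT", a female-male comparison of the same signals, and a comparison of three positions within each of two muscles.

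**The concern.** Twelve locations on one person share that person's physiology and skin, the examiners and the session. A rule that declares them independent lets 10 volunteers be counted as up to 120 observations.

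This matters most where the other variable belongs to the person. Walk distance has one value per volunteer per visit, and sex has one value per volunteer. Pooling locations copies that single value into every row and treats the copies as new evidence. The p-value, and the 95% interval planned for the correlation, then no longer have their stated error rates.

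The protocol says the results are needed to plan later studies in children with neuromuscular disorders, so a walk-distance or sex association declared on noise could carry forward.

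**Working it through.** **Inputs from the documents.** 10 volunteers (Protocol section 9); 3 positions × 2 muscles × 2 sides = 12 locations (sections 7 and 10), so 10 × 12 = 120 rows per session; significance level 0.05 (SAP). There is no planned figure to reproduce, because both documents say that no sample size was calculated.

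**Assumptions, not in the documents.** Locations are pooled as rows; tests are two-sided; all locations on one person have the same correlation ρ, tried at 0.1/0.3/0.5. V is the variance of fixed mean differences between the pooled locations, divided by the volunteer-plus-residual variance. V = 0 means equal mean signal everywhere.

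**Step 1: effective sample size, V = 0.** Design effect = 1 + (12 − 1)ρ = 2.1/4.3/6.5. Effective n = 120 / design effect = 57/28/18.5, against a nominal 120.

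**Step 2: what the nominal n does.** The smallest |r| with p < 0.05 is t/√(n − 2 + t²), where t is the 97.5% point on n − 2 degrees of freedom. It is 0.18 at n = 120, 0.25 at 60, 0.44 at 20 and 0.63 at 10. The Fisher interval tanh(atanh r ± 1.96/√(n − 3)) at r = 0.3 is 0.13 to 0.45 with n = 120, and −0.41 to 0.78 with n = 10.

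**Step 3: false positives for the 6-MWT Pearson correlation.** Simulation with no true association, 20,000 to 40,000 runs per setting, nominal 5%, ρ = 0.1/0.3/0.5. Independent runs differ by about one point.

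| Locations pooled per volunteer | V = 0 | V = 1 | V = 2 |
|---|---|---|---|
| 12 | 18/36/47% | 5–6/19/28% | 2/10/18% |
| 6 | 11/23/32% | 2/8/14% | 1/3/6–7% |

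Two locations with V = 0 give 6/9/12%. One mean per volunteer gives 5% throughout. Coverage of the 95% interval with 12 locations and V = 0 is 82/64/53%; with one value per volunteer it is 95%.

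**Step 4: why the direction can change.** Ignored location differences enlarge the naive error variance. With m locations, the true variance exceeds the naive one roughly by the factor [1 + (m − 1)ρ]/(1 + V). Pooling is therefore too optimistic when V < (m − 1)ρ: below 1.1/3.3/5.5 for 12 locations, and below 0.5/1.5/2.5 for 6. The table agrees. Six locations with ρ = 0.1 and V = 1 give a factor of 1.5/2 = 0.75 and a 2% rejection rate.

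**Step 5: female-male comparison.** The SAP names no two-group test. With an assumed two-sample t-test, 5 v 5, 12 locations and V = 0, the rates are 18/36/47%. One mean per volunteer gives 5%.

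**Step 6: paired exercise and two-week tests.** A stable person effect cancels in the difference. If raw signals correlate at 0.5 but the changes are independent, the pooled paired test stays at 5.0%. If the changes themselves correlate at 0.1/0.3/0.5, 12 pooled locations give about 18/35/46%. The documents do not say which applies.

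**Step 7: uses that are valid as named.** A paired test with one location per person, and a Friedman test with one set of three positions per person, both have n = 10 and no clustering problem.

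**Step 8: averaging before the ICC.** With errors independent between locations, the ICC of a six-location mean is T/(T + E), where T = ICC × [ρ + (1 − ρ)/6] and E = (1 − ICC)/6. For a single-location ICC of 0.6 and ρ = 0.1, T = 0.150 and E = 0.067, giving 0.69. At ρ = 0.3 and 0.5 the result is 0.79 and 0.84.

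**The case against.** The strongest reply is that the SAP never says locations are pooled. The sentence before the rule already uses the word independent of muscle regions, so the rule may mean only that each location is a distinct site, analysed separately. On that reading n = 10 per test and nothing is inflated. This stands as a limit: a reader might infer that 120 rows will be analysed, and the documents do not say so. It does not remove the gap, because the plan's only statement on dependence permits pooling and no n is given.

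A second reply is that pooling need not be optimistic. This also stands. The SAP says that differences between muscles and positions are unknown, and Step 4 shows that such differences shrink or reverse the inflation. A blanket claim of too many false positives is not supported.

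Third, a reader might infer that the primary before-and-after comparison is invalid. The documents do not support that, because it is affected only if changes correlate within a person.

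Finally, the study is an exploratory pilot, and the two exposed analyses are secondary objectives. That lowers the consequence, but both documents still declare significance at 0.05.

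**Conclusion.** The independence statement cannot be assumed true for 12 locations on one person, and the missing unit of analysis is a defect on any reading. If locations are pooled, the error rate of the 6-MWT correlation and of the female-male comparison, and the coverage of the correlation's 95% interval, are wrong in a direction and size that the plan does not control.

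With 12 locations and ρ from 0.1 to 0.5, false positives for the correlation run from 18% to 47% if location means are equal, and from about 2% to 18% if location variance is twice the volunteer-plus-residual variance. Optimism is the likely direction at moderate ρ with small location differences. Small differences are what the protocol itself hypothesises within one muscle; six equal-mean locations there (three positions, two sides) give 11/23/32%.

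These figures rest on pooling, an equal ρ and the stated V, none of which the documents give. The point should be fixed before analysis.

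**What to change.** Delete the independence sentence, name the volunteer as the unit of analysis, and state n for each test.

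1. **6-MWT correlation (per visit), female-male comparison, and exercise and two-week paired tests.** Average to one value per volunteer per muscle and condition (n = 10), and name the two-group test for sex. A mixed model is an alternative only with fixed effects for muscle, side and position, random effects for volunteer and volunteer-by-exercise or volunteer-by-visit, and small-sample degrees of freedom. It may be hard to fit with 10 volunteers and is conservative when ρ is near 0 (1.8% rejection for the exercise effect at ρ = 0 with 12 locations), so averaging is preferable.
2. **Three-position comparison.** Keep the positions, average over sides within each muscle, and use repeated-measures ANOVA or Friedman with the volunteer as block (n = 10).
3. **Examiner and repeat-scan agreement.** Keep the ICC at single-location level, computed per location (n = 10) or with an interval that allows for clustering by volunteer. Do not average locations first, because that measures a different reliability (Step 8).

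The cost is SAP wording. No new data are needed, and SPSS, already named, can run these analyses. The nominal n falls to 10 and p-values become less favourable.

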The MSOT data collected so far seem promising to enable therapy monitoring in DMD patients. Preliminary work by other groups has already demonstrated a very good precision and reproducibility of MSOT. However, it has not yet been investigated to what extent 1) previous physical activity, 2) different measurement positions of the muscle, 3) different examination dates and 4) intra- and interrater variability influence the measurement results. Especially molecular changes immediately after the 6-MWT are relevant for studies in muscle patients with DMD.

In this first pilot study, the aim is to investigate in healthy adults whether increased exercise alters haemoglobin values, the collagen content remains constant and repeated measurements at different muscle positions by different investigators provide consistent measurement results over time. This information is essential for further studies of children with neuromuscular disorders to properly evaluate a possible response to therapy.

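### The planned paired tests, ANOVA/Friedman and undefined ICC do not estimate how much examiner, time, exercise, position and scan error each contribute, although the crossed design largely allows it

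*SAP*

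**What the plan says.** The open question in the Protocol (section 3, repeated in substance in section 5) is how far four sources affect the measured values: "to what extent 1) previous physical activity, 2) different measurement positions of the muscle, 3) different examination dates and 4) intra- and interrater variability". The SAP turns this into its primary outcome: reproducibility of the muscle spectra across examiner, time, exercise and position.

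The design is set out in the Protocol, section 9 (Participant number) and section 10 (Measurements):

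- "It is planned to examine a total of 10 healthy volunteers".
- There are three positions in each of two muscles on both legs, so 12 sites.
- "The examination is performed by two independent examiners directly one after the other".
- "Each examiner performs two repetitive scans per muscle position".
- After the walk test: "Afterwards another examination with MSOT is carried out analogous to the above mentioned procedure".
- For the second visit: "The same procedure is repeated after 14 days".

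For the analysis, the SAP states: "MSOT signals are compared matched manner using a paired t-test when parametric and a Wilcoxon matched-pair signed rank test when non-parametric". ANOVA or Friedman serves three or more groups. Pearson and Spearman correlations are added, as is an ICC graded by Landis and Koch. Multiple scans are averaged, and anatomical locations are taken to be independent. Section 12 of the Protocol names only a t-test between the two timepoints and Pearson correlation. Neither document names a multi-factor model, a mixed model or variance components. Neither says which levels of the other factors are fixed, averaged or pooled in a given comparison.

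**The concern.** The layout can separate the sources of variation, but the stated analyses take them comparison by comparison. A paired comparison over two weeks yields a mean difference and an SD of differences. That SD pools real change in the volunteer, a different probe placement and scan noise. If it is large, the analysis does not show which of the three is responsible.

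This matters because the Protocol (sections 5 and 11) says the results are needed to plan later studies, including those in children with neuromuscular disease. Whether such a study should take more scans, keep to one examiner or add visits depends on which source dominates.

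Two further sentences in the SAP add to the problem. Averaging repeat scans, with no exception stated, removes the within-examiner differences that three hypotheses and one secondary objective in section 6 of the Protocol depend on. Taking sites as independent ignores that 12 sites belong to one volunteer.

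**Working it through.** The documents give no variance, effect size or sample-size derivation, so there is no planned figure to reproduce. All variance components below are assumptions.

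1. **Size of the design.** 10 volunteers x 2 visits x 2 sessions (before and after the walk) x 12 sites x 2 examiners x 2 scans = 1,920 scans, or 960 values after averaging scan pairs. The layout is crossed if it is complete and the same two examiners attend both visits, which the text does not state.

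2. **What matching removes.** In simulated data from this layout, shifts of 5 (visit), 3 (examiner) and 0/2/4 (position) left the matched exercise differences unchanged (largest change 2e-15). In one simulated data set, the paired t-test on volunteer means and the crossed-ANOVA F-test of exercise agreed exactly (t² = F = 3.129, p = 0.111). Over 4,000 simulated studies its type I error was 5.3%.

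3. **What stays mixed.** Let V be the date variance, E examiner relocation and S single-scan error, as shares of single-scan variance. For one site, the same examiner and the mean of two scans:
   - variance of the two-week difference = 2(V + E + S/2)
   - date share = V/(V + E + S/2)

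   Assumed central values are V = 0.05, E = 0.05, S = 0.20. Assumed ranges are V and E 0.02–0.10, S 0.10–0.30.
   - Central: 0.05/(0.05 + 0.05 + 0.10) = 25%.
   - Lowest: 0.02/(0.02 + 0.10 + 0.15) = 0.02/0.27 = 7%.
   - Highest: 0.10/(0.10 + 0.02 + 0.05) = 0.10/0.17 = 59%.
   - If date has both a volunteer-wide and a site-specific part of 0.05 each: 0.10/(0.10 + 0.05 + 0.10) = 40%.

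4. **Why the paired SD cannot decide.** Two cases inside these ranges:
   - V = 0.10, E = 0.02, S = 0.10: variance 2 x 0.17 = 0.34, date share 59%.
   - V = 0.02, E = 0.05, S = 0.20: variance 2 x 0.17 = 0.34, date share 0.02/0.17 = 12%.

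   The SD of differences is the same, but the first is mainly date and the second mainly placement and scan noise.

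5. **What the ICC leaves open.** A second simulation used these assumed variances: volunteer 1, volunteer-by-site 0.3, volunteer-by-visit 0.2, volunteer-by-exercise 0.2, volunteer-by-examiner 0.05, scan 0.3, and between leg/muscle locations 1.0 (0.5 for the examiner-shift comparison and in steps 2 and 6). With identical examiner error, the mean inter-examiner ICC was 0.80 (single scan, one site), 0.87 (mean of two scans, one site) and 0.91 (120 volunteer-sites pooled). With a systematic examiner shift of 1.0, the agreement ICC was 0.67 and the consistency ICC 0.87.

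6. **Independence of sites.** If the 10 x 12 = 120 volunteer-sites are tested as independent pairs, the type I error for exercise is 0.52 to 0.55 under the variances of step 5, against about 0.05 on volunteer means.

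**The case against.** The strongest reply is that the components can be had from analyses already planned. Under the model of step 3, the same-examiner repeat, between-examiner and two-week differences have variances 2S, 2(E + S/2) and 2(V + E + S/2). With the central values these are 0.40, 0.30 and 0.40, and subtraction gives V = (0.40 − 0.30)/2 = 0.05. That is correct, and it shows that the data suffice. But the SAP plans no such subtraction and no intervals for its results, and its averaging sentence, read literally, removes the first of the three quantities.

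Second, this is an exploratory pilot, most objectives in section 6 of the Protocol are single-factor comparisons, and no document promises a ranking of sources. This limits the severity. It does not remove the point, because the SAP itself makes reproducibility across the four factors primary.

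Third, a reader might infer three stronger things:

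- *Each comparison is distorted by the other factors.* It is not: step 2 shows that their main effects cancel. Interactions and scan error remain, and the paired SD accounts for them.
- *With no true date effect, noise would be reported as change over time.* The planned test is of a mean difference. Noise widens its SD, but a paired test on volunteer means keeps its error near 5%. Inflation arises only if sites are used as independent pairs.
- *The question of extent is left unanswered.* The SDs, the ICC and the ANOVA answer it in part, and a multi-factor ANOVA is not expressly excluded.

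**Conclusion.** The concern holds in a limited form. The plan does not specify an analysis that estimates the size of each source, and it leaves the form and unit of the ICC open. In a two-week difference, volunteer-by-visit variation, examiner relocation and scan error stay mixed. Under the assumed ranges, date accounts for 7% to 59% of that variance. The paired SD alone does not narrow this, as two cases with the same SD and shares of 12% and 59% show.

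These percentages are illustrative, because the documents give no components. The conclusion that the sources are not separated does not depend on the particular values. It does assume a complete layout and the same two examiners at both visits. The 0.52–0.55 error rate applies only if the independence sentence means that sites serve as the unit of testing, which the SAP does not say outright.

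Paired tests on volunteer means are valid. This is a cheap improvement to the plan, not a flaw that invalidates the study.

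**What to change.** Add to the SAP, as the main reproducibility analysis, one linear mixed model per signal fitted to scan-level values:

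- **Fixed effects:** session, visit, examiner, muscle, side and position. With only two examiners, the examiner's mean shift is better fitted as fixed.
- **Random terms:** volunteer, volunteer x visit, volunteer x location, volunteer x location x visit, and residual scan error. Add an examiner relocation term only if it can be estimated. Larger sets are fragile with 10 volunteers.
- **Report:** the SD per source and the factor differences, each with a 95% interval that treats the volunteer as the independent unit.
- **ICC:** derive it from this model. State agreement or consistency, single or averaged scan, and the unit.
- **Averaging:** exempt the intra-examiner comparison.
- **Paired tests:** keep them as secondary, on volunteer-level means, and say which levels of the other factors are averaged or fixed. Drop the independence of sites as a basis for testing.

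The cost is SAP wording and some more analysis work. No new data are needed, and SPSS, which the SAP already names, fits such models.

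There are two limits. Volunteer-level components will be imprecise: in simulated pre-walk data (960 scans) a true volunteer-by-visit variance of 0.05 was estimated anywhere from about 0.008 to 0.113 (95% sampling range). And no model separates examiner from scan order or time since exercise if the order is fixed. The readable text gives no order rule, so the order should be recorded and stated.

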#### ***Statistical methods:***

The data are given as mean value with standard deviation. Correlations are specified with the parametric Pearson correlation coefficient (R). According to the distribution between timepoint 1 and timepoint 2, the differences of the mean values are statically examined with a parametric T-test. In all analyses, an error level of <0.05 is considered statically significant.

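### The SAP's independence rule is wrong for muscle positions within one volunteer, conflicts with its matched tests, and leaves the type of ANOVA open

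*SAP*

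**What the plan says.** The SAP gives one rule for comparisons with more than two levels: "For the comparison of three or more groups analysis of variance (ANOVA) and for nonparametric distribution Friedman Test is used". It does not say which form of ANOVA is meant and names no subject factor. Slightly earlier it states, without qualification, "All anatomical locations are considered independent". Between these two statements it prescribes matched tests for two-level comparisons (paired t-test, or Wilcoxon for matched pairs). It plans an intraclass correlation coefficient (ICC) in addition.

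The Protocol, under Measurements, says that "all study participants are imaged by MSOT at 3 positions of 2 anatomical muscle regions on both sides (right and left"), so every volunteer contributes all three positions of each muscle. Comparing those positions is listed under Secondary objectives, and the Hypotheses state for three signals that there is no difference within a muscle. No equivalence margin is given. The SAP also lists muscle position among the variables in its primary reproducibility outcome. The Protocol's Statistical methods section names only a t-test and the Pearson correlation, so it does not settle how three positions are to be tested.

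**The concern.** Three positions in one muscle of one person share that person's skin, perfusion and muscle composition, so their signals should be expected to correlate. A rule that treats them as independent points the analyst towards an ANOVA that ignores who was measured. Differences between people, which say nothing about position, then inflate the error term and the test becomes too conservative.

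The direction matters because the hoped-for result is no difference, and an insensitive test errs towards it. The Protocol says that this information is needed to plan studies in children with neuromuscular disease, so a missed position effect could carry over into where the probe is placed in those studies.

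The two distributional branches could also rest on different designs. Friedman keeps the matching. If the ANOVA does not, a Shapiro-Wilk result decides whether the same 10 people are analysed as matched or unmatched.

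**Working it through.** The plan gives no power, SD, effect size or correlation ("Therefore, no sample size calculation was performed"), so it has no figure to reproduce. The check asks what follows if the ANOVA is run as one-way.

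**Inputs from the documents**
- Volunteers: n = 10 (Protocol, Participant number: "It is planned to examine a total of 10 healthy volunteers").
- Positions: 3 per muscle, all in each volunteer (Protocol, Measurements).
- Significance level: 0.05 (Protocol, Statistical methods; SAP).

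**Assumptions**
- Correlation ρ between positions within a volunteer: 0 to 0.9, equal for all pairs.
- Normal data, total variance 1, one muscle on one side.
- One position shifted by 0.5 or 1.0 total SD, the other two equal.

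**Step 1: error terms.** The residual sum of squares is distributed as (1−ρ)·χ² on 18 df, and the between-volunteer sum of squares as (1+2ρ)·χ² on 9 df. Repeated-measures ANOVA uses only the first, with expected mean square 1−ρ. One-way ANOVA pools both: [18(1−ρ) + 9(1+2ρ)]/27 = 27/27 = 1. Its denominator is therefore too large by the factor 1/(1−ρ), which is 2 at ρ = 0.5 and 10 at ρ = 0.9.

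**Step 2: type I error of the one-way test.** The critical value is c = F(0.95; 2, 27) = 3.354, so 2c/27 = 0.2485. Because P(χ² on 2 df > x) = exp(−x/2), the true size is

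(1 + 0.2485)^(−9) × [1 + 0.2485·(1+2ρ)/(1−ρ)]^(−4.5)

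- ρ = 0: 1.2485^(−13.5) = 0.050, as it should be.
- ρ = 0.3: 0.1357 × 1.568^(−4.5) = 0.1357 × 0.1322 = 0.018.
- ρ = 0.5: 0.1357 × 1.994^(−4.5) = 0.1357 × 0.0448 = 0.006.
- ρ = 0.7: 0.1357 × 2.988^(−4.5) = 0.1357 × 0.0073 = 0.001.
- ρ = 0.9: 0.1357 × 7.957^(−4.5) = 0.00001.

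Simulation at 40,000 runs per cell gave 1.9%, 0.7%, 0.1% and below 0.1%, which agrees.

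**Step 3: power for a 0.5 SD shift.** The means are 0, 0 and 0.5, with squared deviations summing to 0.1667. For repeated-measures ANOVA, λ = 10 × 0.1667/(1−ρ) = 1.667/(1−ρ), referred to the noncentral F on 2 and 18 df (critical value 3.555). One-way power is simulated.

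| ρ (assumed) | λ | Repeated-measures power | One-way power | One-way type I error |
|---|---|---|---|---|
| 0.3 | 2.38 | 23% | 12% | 1.8% |
| 0.5 | 3.33 | 31% | 9% | 0.6% |
| 0.7 | 5.56 | 48% | 5% | 0.1% |
| 0.9 | 16.67 | 93% | 2–3% | <0.1% |

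At ρ = 0 the two tests perform alike (17% repeated-measures, 18% one-way).

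**Step 4: larger shift.** With one position shifted by 1.0 SD, one-way power is about 56%, almost regardless of ρ. Repeated-measures power at ρ = 0.5 is 86% (λ = 10 × 0.6667/0.5 = 13.33).

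**Step 5: the choice of branch.** At ρ = 0.9 with a 0.5 SD shift, Friedman has about 80% power. In 78% of the simulated data sets Friedman was significant and one-way ANOVA was not.

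**The case against.** The strongest reply is that the SAP never specifies a one-way ANOVA. The sentence just before the ANOVA rule says that signals are compared in matched fashion, and the nonparametric counterpart is Friedman, whose natural parametric partner is repeated-measures ANOVA. This stands. A reader might infer that the SAP has chosen a between-groups test and thrown the matching away, but the documents do not say so. What they contain is an unresolved conflict: the only sentence describing how locations relate to each other calls them independent.

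A second reply is that the independence sentence may mean muscle regions and not positions, since the SAP uses separate terms. The sentence is unqualified, however, and two muscles or two legs of one volunteer are not independent of each other either. It is also fair that the SAP does not tie the ANOVA rule to positions. The design offers other comparisons with more than two levels, such as the four combinations of visit and exercise state.

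A reader might also infer that the hypothesis of no difference becomes almost impossible to refute. The figures do not support that. The heavy loss is confined to shifts of about 0.5 SD or less with correlations of about 0.5 or more. If both legs are entered as 20 rows, a 1.0 SD spread across equally spaced positions is detected 82% to 91% of the time.

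Finally, matching alone does not establish sameness. At ρ = 0.5, repeated-measures ANOVA still misses a 0.5 SD shift about 69% of the time (100 − 31). That also stands, and it shapes the fix. The study is exploratory, and the planned ICC means that reproducibility does not rest on the ANOVA alone.

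**Conclusion.** The concern holds as a conflict in the SAP that needs correcting, with a conditional consequence. The independence rule is untrue for positions within one volunteer and is inconsistent with the matched tests around it; the form of ANOVA is unstated. This is more than a missing detail, because following the rule literally yields an ordinary ANOVA.

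The size in the table applies only if a one-way ANOVA is actually run, and it depends on assumed correlations, normality, equal correlation between positions, and one leg with 10 volunteers. Since the true correlation is unknown, the real loss could lie anywhere from none to nearly all of the power to see a 0.5 SD shift. The error would lean towards the conclusion the Protocol hypothesises.

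**What to change.** In the SAP:

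- Delete the independence sentence, or restrict it so that it does not cover measurements within the same volunteer.
- For positions, name a repeated-measures ANOVA with volunteer as subject and position as within-subject factor, sphericity-corrected and run separately for each muscle. A mixed model with the same structure would also serve.
- State how the two legs enter: averaged, or as a further within-subject factor.
- Keep Friedman as the matched counterpart.
- Report pairwise position differences with 95% confidence intervals, and base any statement of no difference on those intervals and not on a non-significant p-value.

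The cost is SAP wording. The measurements and number of volunteers stay the same, and no new data are needed.
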